2.2.6 Key secondary analysis

There are three key secondary efficacy variables defined in this study.

All key secondary variables will be analyzed using the FAS and PPS populations, and will be repeated for the subgroups provided in Table 2-3 by adding the subgroup and the treatment by subgroup interaction terms to the model for time to event endpoints.

Whenever the event or visit time needed for defining the time-to-event or censoring date and time is missing or incomplete, an imputation rule for missing/incomplete time will be applied. More details about the imputation rule are presented in [Section 2.2.9](#).

2.2.6.1 Time to all-cause death through Day 180

Time to all-cause death will be calculated as:

Time-to-event (days) = date of all-cause death – randomization date,

The analysis will be performed similarly to primary endpoint.

For those subjects without events, the censoring date will be the earliest in the following dates:

- **180 days**
- **Date subject withdrew consent to all follow-up (if no subsequent vital status documented)**

Note: in accordance with local laws and regulations, vital status may be publically available

- **Date of subject's last visit or contact or vital status**

A covariate-adjusted Cox-regression model similar to the sensitivity analysis of primary efficacy variable will also be performed as sensitivity analysis.

2.2.6.2 Length of total hospital stay (LOS) during the index AHF hospitalization

Length of stay will be defined as the index hospitalization discharge date and time minus the randomization date and time, whereas time is used for better precision and converted to days.

Subjects still in the hospital at Day 60 will be censored at Day 60. Subjects who die during the initial hospitalization will be assigned the maximum length of stay (including those censored at Day 60) plus 1 day.

Subjects missing the discharge date, such that a determination of the length of stay cannot be calculated, will be assigned the mean length of stay over all subjects with not missing discharge date.

Treatment groups will be compared using a Wilcoxon rank sum test.

For subgroup analysis, a p-value for the test of the treatment by subgroup interaction term will be based on a two-way model with treatment, subgroup and treatment-by-subgroup interaction using rank-transformed data.

The van Elteren extension to the Wilcoxon rank sum test will also be carried out stratifying for region.

2.2.6.3 Time to first occurrence of the composite endpoint of CV death or rehospitalization due to heart failure (HF)/renal failure (RF) through Day 180

Time to event will be calculated as date of first event of adjudicated CV death or adjudicated rehospitalization due to HF/RF minus randomization date in days. If the reason for adjudicated rehospitalization is unknown, it will be considered as HF or RF.

The analysis will be performed similarly to primary endpoint.

For subjects without events the censoring date will be the earliest in the following dates:

- **180 days**
- **Date subject withdrew consent to all follow-up**
- **Date of subject's last visit or contact**
- **Date of non-CV death**

In addition, the estimates with 95% CI at 30, 60, and 90 days from the Kaplan-Meier method will be provided. Of note estimates at 60 and 90 days are considered as exploratory analyses.

The analysis for one of components of the composite endpoint, time to rehospitalization due to HF/RF through Day 180, will also be performed. The estimates with 95% CI and p-value at Day 180 from the Kaplan-Meier method will also be provided.

[figure not shown]

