### 3 Investigational plan

#### 3.1 Study design

Figure 3-1 Study design

- † Weight-range based dosing regimen for serelaxin and matching placebo (see [Table 5-3](#))
- \*If Discharge Visit coincides with a scheduled visit, only the Discharge Visit will be performed.
- Presentation starts as the earliest of (1) time of presentation either at the ER/ED, ICU/CCU or ward, (excludes EMS or other pre-hospital care); or (2) time of first IV loop diuretic prior to arrival at the hospital (this includes outpatient clinic, ambulance, or hospital including emergency department) for the treatment of the current AHF episode.

This study is a multicenter, randomized, double-blind, placebo-controlled, event-driven phase IIIb clinical trial designed to evaluate the efficacy and safety of an intravenous infusion of serelaxin when added to standard therapy in AHF patients. After assessing eligibility during the screening period, patients who meet the study inclusion and exclusion criteria will be randomized 1:1 to receive an intravenous infusion of either serelaxin or matching placebo in a double-blind manner for up to 48 hours ([Figure 3-1](#)). Potential study candidates are those patients hospitalized for AHF, who have received at least 40 mg intravenous furosemide (or equivalent) prior to screening, with dyspnea at rest or minimal exertion, systolic BP  $\geq 125$  mmHg at the time of screening, and mild to moderate renal impairment measured as an estimated eGFR of  $\geq 25$  and  $\leq 75$  mL/min/1.73m^2 by sMDRD formula ([Levey et al, 2003](#)). These patients must be randomized **within 16 hours** of presentation, (presentation starts as the

earliest of (1) time of presentation at either the ER/ED, ICU/CCU or ward, (excludes EMS or other pre-hospital care); or (2) time of first IV loop diuretic for treatment of the current AHF episode prior to arrival at the hospital (this includes outpatient clinic, ambulance, or hospital including emergency department).

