2.2.6.4 Multiple testing procedure

The key secondary efficacy variables of all-cause mortality through Day 180 will not be formally incorporated in a multiple testing procedure. It will be tested with a full α (two-sided) by itself if one of the primary endpoints, CV death or WHF is statistically significant.

The primary endpoints of CV death and WHF will be tested first. If at least one of the primary endpoints is significant, the other two key secondary variables will be tested using a sequentially rejective multiple testing procedure in testing LOS and composite of CV death or rehospitalization due to HF/RF (CVDR) in controlling overall α ([Bretz, et al 2009](#)). [Figure 2-1](#) illustrates this multiple testing procedure for two primary and two key secondary variables

with strong control of overall α level of 5%. Note: although CV death will be tested initially at 0.02 (one-sided) significance level and WHF at 0.005 (one-sided) significance level, the final significance level for CV death and WHF will be updated according to the graphical testing strategy incorporating two secondary variables, LOS and CVDR, as depicted in below figure.

Figure 2-1 **Sequentially rejective multiple testing procedure for two key secondary efficacy variables**

Where CVD is CV death, WHF is worsening heart failure, LOS is length of hospital stay, and CVDR is a composite variable of CV death or rehospitalization due to heart failure or renal failure.

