2.4 Interim analyses

It is planned to establish an external and Independent Data Monitoring Committee (DMC) to monitor subject safety data on a regular basis during the course of the study. For this study, it is planned that the DMC will review safety data on a regular frequency, e.g., every six months. DMC may request additional safety data review. Such safety analyses do not inflate the type I error for the primary efficacy hypothesis testing and thus require no multiplicity adjustments.

It is planned to have one formal interim efficacy analyses. The cut-off for this interim analysis is planned when the information fraction (number of confirmed CV deaths relative to the targeted total number of confirmed CV death at the study completion) of 60% is achieved (corresponding to 329 CV deaths). Some adjustment to the time of interim analysis may be made to coincide with the regular DMC meetings. One-sided tests will be performed and appropriate statistical adjustments for the interim analysis actually performed will be made to ensure the overall one-sided type I error of 0.02 (Lan-DeMets spending function to match an O'Brien-Fleming stopping boundary). For the interim analysis, the analysis dataset will comprise all subjects who were randomized before the cut-off date.

The trial may be concluded early for efficacy, if a significant difference between two treatment arms for the number of CV deaths is achieved by crossing the pre-specified boundary at interim analysis. Interim analysis will be performed by an external independent statistician at an external data analysis center, who will not be involved in the study conduct. The results will be reviewed by the independent DMC. Investigators and others who are involved in the conduct of the trial and in the analysis of the final trial results, or who have contact with study centers, will remain blinded to the treatment codes and interim analysis results until all monitoring decisions have been made and the database has been locked for final analysis.

If the DMC recommends stopping the study due to overwhelming efficacy of CV deaths, i.e., crossing the pre-specified boundary and favorable risk and benefit ratio, the multiple testing procedure in [Figure 2-1](#) will be applied and updated as [Figure 2-2](#) below. The significance levels for WHF, LOS and CVDR are 0.6α , 0.2α and 0.2α .

[figure not shown]

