2.5 Sample size and power considerations

The alpha (α) level of 5% is split to CV death at 4% and to WHF at 1%. The sample size calculation is based on the CV death endpoint. This is an event-driven trial with fixed maximum duration of 180 day follow-up period for each patient. In the sample size calculation, the 180-day CV death rate is assumed to be 9.0% in the placebo group, which is about 80% of 11.3% of all cause death observed in the placebo group in the RELAX-AHF study.

The interim analysis will be performed when 329 CV deaths are accrued. At the interim analysis, if Z-score of 2.786 (one-sided nominal $p = 0.0027$) is observed, which corresponds to HR of 0.735 (at least 26.5% RRR), the DMC may recommend to stop the study due to crossing the boundary. If there is no stopping at the formal efficacy interim analysis, the final analysis will need to have a Z-score of 2.072 (one-sided nominal $p = 0.0192$), which corresponds to HR of 0.838 (at least 16.2% RRR), to declare a significant study. ([contact], Cytel Inc., Cambridge MA, 2010).

If the observed overall event rate of the CV death endpoint during the course of the trial is much lower than expected based on the design assumptions (assessed on a blinded basis), adjustments may be made to the number of patients to be randomized in order to achieve the required number of events in the pre-planned timeframe (180 days) and thus to preserve the target study power.

For the sample size of 6,800, the unconditional power for the WHF endpoint and all three key secondary endpoints under various HRs (mean difference for Length of Stay) are summarized in the tables below:

Table 2-10 Assumed effect sizes for worsening heart failure and the key secondary efficacy variables on power calculation

	Assumed HR or mean difference
Worsening Heart Failure (placebo rate: 12.2%)	0.70
	0.80
All cause death (placebo rate: 11.3%)	0.80
	0.816
	0.83
Length of Stay (mean ±SD between placebo and serelaxin: 0.9 ±9.6 day)	0.9 day
	0.7 day
CV death or HF/RF rehospitalization (placebo rate: 34.1%)	0.85
	0.88

Note: Assumed placebo rates for all cause death and WHF and mean difference (mean + SD) in LOS between serelaxin and placebo were based on RELAX AHF study; placebo event rate of CV death or HF/RF rehospitalization was estimated to be 34.1% by assuming an exponential distribution with the same hazard as that observed through Day 60 in RELAX AHF study.

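### The confirmatory length-of-stay test ignores region; promoting the region-stratified test the SAP already plans could add 0 to about 8 points of power

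*SAP*

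**What the plan says.** SAP 2.2.6.2 defines LOS from randomization to discharge, censors at Day 60, gives in-hospital deaths the worst value, and then states: "Treatment groups will be compared using a Wilcoxon rank sum test". Protocol 10.5.1 names the same test, and SAP Table 2-5 lists only the Wilcoxon rank-sum test for LOS.

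The same SAP section ends with a second test: "The van Elteren extension to the Wilcoxon rank sum test will also be carried out stratifying for region". It is given no role in the decision. For ICU/CCU stay (SAP 2.2.7.1) the corresponding test is expressly called a sensitivity analysis; for LOS it carries no label.

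LOS belongs to the graphical procedure covering two primary and two key secondary variables, "with strong control of overall α level of 5" per cent (SAP 2.2.6.4). Region is defined in five groups in SAP Table 2-3. It is a factor or stratum in the signs-and-symptoms Cox model, the biomarker model and the supportive logistic regression for worsening heart failure (WHF). Protocol 5.3 mentions no stratification of the randomization by region.

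**The concern.** If hospitals in different regions keep patients for different lengths of time, the unstratified ranking mixes that spread with the treatment comparison. The van Elteren test ranks within region and removes it. Region is fixed at baseline, already collected and already grouped.

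What is at stake is power for one confirmatory endpoint. It matters most in the 0.7-day scenarios, where the plan's own LOS power is only 72 to 78% (SAP Table 2-11 B).

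**Working it through.** **Inputs from the documents**

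- Sample size: "For the sample size of 6,800, the unconditional power for the WHF endpoint and all three key secondary endpoints under various HRs" (SAP 2.5). Patients are "randomized 1:1 to receive an intravenous infusion of either serelaxin or matching placebo" (Protocol 3.1), so 3,400 per arm.
- LOS: "Length of Stay (mean ±SD between placebo and serelaxin: 0.9 ±9.6 day" (SAP Table 2-10), with 0.7 day as the alternative difference.
- Alpha: "CV death will be tested initially at 0.02 (one-sided) significance level and WHF at 0.005 (one-sided) significance level" (SAP 2.2.6.4).
- After CV death is rejected: "The significance levels for WHF, LOS and CVDR are" 0.6α, 0.2α and 0.2α (SAP 2.4). CV death starts with 0.8α and WHF with 0.2α, so CV death passes on 1/2, 1/4 and 1/4 of its level.
- CV death: HR 0.78, 329 deaths at 60%, final boundary Z = 2.072. WHF: placebo rate 12.2%, HR 0.70 or 0.80. CV death or HF/RF rehospitalization (CVDR): placebo rate 34.1%, HR 0.85 or 0.88.

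**Not given:** the share R² of LOS rank variance explained by region (assumed 0 to 20%), and the remaining edges of the testing graph, because the figures are not shown.

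**Step 1: expected z-scores**

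- LOS: z = δ / (9.6 × √(2/3400)) = δ / 0.2328, so 3.865 for 0.9 day and 3.006 for 0.7 day.
- Time-to-event endpoints: z = |ln HR| × √events / 2.
  - CV death: 329/0.60 = 548.3 events, z = 2.909.
  - WHF: 3400 × (0.122 + 1 − 0.878^HR) gives 711 events (HR 0.70, z = 4.755) or 751 (HR 0.80, z = 3.057).
  - CVDR: 3400 × (0.341 + 1 − 0.659^HR) gives 2,174 events (HR 0.85, z = 3.789) or 2,204 (HR 0.88, z = 3.001).

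**Step 2: reproduce the plan's LOS power.** The four z-scores were put through a simulated graphical procedure (200,000 draws, independent endpoints). WHF was assumed to pass on alpha as CV death does, and each secondary to return half to each primary.

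| WHF HR / LOS / CVDR HR | Table 2-11 B | Recomputed |
|---|---|---|
| 0.7 / 0.9 d / 0.85 | 93 | 93.8 |
| 0.7 / 0.9 d / 0.88 | 92 | 93.4 |
| 0.7 / 0.7 d / 0.85 | 78 | 78.4 |
| 0.7 / 0.7 d / 0.88 | 77 | 77.3 |
| 0.8 / 0.9 d / 0.85 | 87 | 88.0 |
| 0.8 / 0.9 d / 0.88 | 86 | 87.6 |
| 0.8 / 0.7 d / 0.85 | 73 | 73.0 |
| 0.8 / 0.7 d / 0.88 | 72 | 72.0 |

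All values lie within 2 points of the plan.

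**Step 3: stratify.** The LOS z is divided by √(1 − R²), a factor of 1.026 at 5%, 1.054 at 10% and 1.118 at 20%. LOS power (%) through the full procedure:

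| Scenario | R² 0 | 2% | 5% | 10% | 20% |
|---|---|---|---|---|---|
| 0.7 / 0.9 d / 0.85 | 93.8 | 94.2 | 94.8 | 95.7 | 97.2 |
| 0.7 / 0.7 d / 0.88 | 77.3 | 78.1 | 79.3 | 81.5 | 85.7 |
| 0.8 / 0.9 d / 0.85 | 88.0 | 88.4 | 89.0 | 89.9 | 91.4 |
| 0.8 / 0.7 d / 0.88 | 72.0 | 72.8 | 74.0 | 76.1 | 80.2 |

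The gain is 0 points at R² = 0, about 1 to 2 at 5%, 2 to 4 at 10% and 3 to 8 at 20%. It is capped because LOS can be tested only after a primary is rejected, which happened in about 99.7% (WHF HR 0.7) or 93.7% (WHF HR 0.8) of simulated trials. If the secondaries instead pass alpha to each other, the second row runs from 77.8 to 82.0 at 10%, a similar gain.

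**Step 4: simulate the two rank tests directly** (1,500 trials of 6,800 patients, five regions with assumed shares, 0.7 day, one-sided 0.0125, Monte Carlo error about 1 point).

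| R² | Wilcoxon power | van Elteren power | Ratio of mean z |
|---|---|---|---|
| 0 | 76.3 | 76.3 | 2.94/2.94 = 1.00 |
| 5% | 76.1 | 77.9 | 2.99/2.92 = 1.024 |
| 10% | 74.6 | 80.7 | 3.07/2.91 = 1.055 |
| 20% | 75.9 | 84.3 | 3.26/2.93 = 1.113 |

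The z ratios agree with the formula. Under the null (R² 10%, nominal 2.5%) rejection was 2.7% for Wilcoxon and 1.9% for van Elteren, with simulation error 0.4 points. In two cases with regionally varying effects (R² 5%), van Elteren was still 1 to 3 points ahead.

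**The case against.** The strongest reply is that nothing is wrong. The Wilcoxon test is valid, protocol and SAP agree on it, the stratified version is already pre-specified, and the other alpha-controlled tests are also described without strata. All of that stands and limits this to an efficiency suggestion.

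Several stronger readings are tempting, and the documents do not support them:

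- **Regional differences in stay are established.** No section reports LOS by region. The SAP groups two countries with Western Europe because of how medicine is practised there, which makes differences plausible but gives no size.
- **The gain could be nearly 12 points.** At a fixed one-sided 0.005, power at 0.7 day rises from 66.7% to 78.4% when R² is 20%. But 66.7% lies below every LOS power in Table 2-11 B, because the full procedure often tests LOS at a higher level.
- **CVDR would benefit materially.** In Table 2-11 B, moving from 0.9 to 0.7 day cuts LOS power by 14 to 15 points, while CVDR power moves only 0 to 2 (93 to 93, 79 to 77, 87 to 86, 73 to 72).
- **The switch is free because the analysis is already programmed.** The documents say only that the test will be carried out. Protocol 10.5.1 names the Wilcoxon test, so an amendment under Protocol 12.1 is needed.
- **ICU/CCU stay should change too.** That endpoint is outside the multiplicity control (SAP Table 2-5), so the switch would have no confirmatory effect.

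**Conclusion.** The point holds as an optional improvement. The confirmatory LOS test is valid but leaves any regional variation in LOS as noise. Making the planned van Elteren test confirmatory would raise LOS power by 0 to about 8 points for an assumed regional share of 0 to 20%; for example, from 77.3% to 81.5% at a 10% share with WHF HR 0.7, LOS 0.7 day and CVDR HR 0.88. If region explains nothing, no loss is measurable with 6,800 patients.

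The size rests on the assumed share, on assumed edges where the figures are missing, and on endpoints simulated as independent. A gain is not guaranteed if treatment effects differ strongly between regions. It is worth considering, not something the plan must change.

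**What to change.** Before unblinding, amend SAP 2.2.6.2, SAP Table 2-5 and Protocol 10.5.1 so that the van Elteren test stratified by the five regions of SAP Table 2-3 is the single confirmatory LOS test in Figure 2-1 (and in its early-stopping update, Figure 2-2). Label the unstratified Wilcoxon test as the sensitivity analysis. Freeze the country grouping at the same time, since SAP Amendment 2 was still updating it. Pooled LOS data without treatment codes could be used first to see how much region explains.

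The change needs no extra patients, data or alpha. It costs a written protocol amendment with IRB/IEC approval and, where required, Health Authority approval, plus a SAP amendment. The comparison also becomes a within-region one, and the report should say so.

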2.2.6.4 Multiple testing procedure

The key secondary efficacy variables of all-cause mortality through Day 180 will not be formally incorporated in a multiple testing procedure. It will be tested with a full α (two-sided) by itself if one of the primary endpoints, CV death or WHF is statistically significant.

The primary endpoints of CV death and WHF will be tested first. If at least one of the primary endpoints is significant, the other two key secondary variables will be tested using a sequentially rejective multiple testing procedure in testing LOS and composite of CV death or rehospitalization due to HF/RF (CVDR) in controlling overall α ([Bretz, et al 2009](#)). [Figure 2-1](#) illustrates this multiple testing procedure for two primary and two key secondary variables

with strong control of overall α level of 5%. Note: although CV death will be tested initially at 0.02 (one-sided) significance level and WHF at 0.005 (one-sided) significance level, the final significance level for CV death and WHF will be updated according to the graphical testing strategy incorporating two secondary variables, LOS and CVDR, as depicted in below figure.

Figure 2-1 **Sequentially rejective multiple testing procedure for two key secondary efficacy variables**

Where CVD is CV death, WHF is worsening heart failure, LOS is length of hospital stay, and CVDR is a composite variable of CV death or rehospitalization due to heart failure or renal failure.

2.2.7 Other secondary analysis

Other secondary efficacy variables comprise:

2.2.7.1 Length of ICU and/or CCU stay for the index AHF hospitalization

The days stayed in ICU/CCU will be obtained from eCRF page directly. If subjects die during the initial hospitalization, the maximum number of days plus 1 day in the ICU/CCU over all subjects will be assigned.

The length of ICU and/or CCU stay for the index AHF hospitalization will be analyzed similarly to the length of hospital stay, i.e., it will be compared using a Wilcoxon rank sum

test. As a sensitivity analysis, the van Elteren extension to the Wilcoxon rank sum test will also be carried out stratifying for region.

2.2.7.2 Change from baseline in congestive signs and symptoms of HF through Day 5

Detailed criteria to assess subject's signs and symptoms (dyspnea on exertion, orthopnea, edema, rales, and jugular venous pulse) of heart failure can be found in protocol Appendix 15.

Subjects who die or have a worsening heart failure event (either during the index hospital or rehospitalization due to heart failure) will have their score imputed to be the worst observed score in any subject at any time point in the respective analysis population carried forward from the day of death or WHF regardless of whether their original data are missing through Day 5. For patients who are alive with missing values, the last preceding non-missing value will be used for imputation.

A time-to-event (response defined as ≥ 1 point improvement from baseline) analysis will be applied to provide treatment comparisons. Hazard ratios (serelaxin/placebo) of being a responder for each of the signs and symptoms variables will be estimated using a Cox regression model stratified by region with treatment as a factor.

Since the assessment only occurs on the scheduled visits, the nominal scheduled day will be used directly to determine the time to event with exact handling of ties.

For those subjects without events, the censoring date will be the earliest in the following dates:

- **6 days**
- **Date subject withdrew consent to all follow-up**
- **Date of subject's last visit or contact**

Change from baseline in congestive signs and symptoms of HF through Day 5 will be analyzed by displaying the percentage of subjects in each category by treatment and time points for each of the signs and symptoms variables. The scores will be presented as both categorical and continuous statistics (i.e., rales will be defined as 0, 1, 2, 3 for its 4 categories; jugular venous pulse will be defined as 0, 1, 2 for its 3 categories). Change from baseline will be computed as the baseline value subtracted from the post-baseline value. Treatment groups will be compared with respect to change from baseline at each time point using Wilcoxon rank sum tests.

2.2.7.3 Change from baseline in selected biomarkers from baseline through Day 14 in a subset of randomized subjects

[figure not shown]
A biomarker substudy as measured by a core laboratory will be conducted to enroll at least 1600 subjects.

[figure not shown]
Change from baseline through Day 14 will be performed on the key biomarkers high sensitivity troponin T, cystatin C and NT-proBNP using a repeated measurement model. It is anticipated that the assumption of normally distributed residuals for biomarkers may not hold. Therefore, the model will be performed on log-transformed biomarker. Treatment group, visit (Day 2, Day 5 and Day 14) and region will be fitted as factors and log-baseline biomarker will

[figure not shown]
be fitted as a continuous covariate. Treatment group by visit and visit by log baseline will be included as interaction terms in the model.

The analysis will be presented by treatment group and visit (Day 2, Day 5 and Day 14). The detailed analysis of changes in biomarkers and analyses of associations of baseline biomarker levels with clinical outputs are described in the separate biomarker statistical analysis plan.

Of note the discharge visit for biomarkers will be mapped to Day 2, Day 5 (within +/- 1 day window) or Day 14 (within +/- 3 days window) if Day 2, Day 5 or Day 14 visits are missing.

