#### **6.4.4 Other efficacy assessments**

##### **6.4.4.1 Assessment of AHF signs and symptoms**

The investigator or appropriately qualified designee will evaluate the signs and symptoms of heart failure, including patient's dyspnea on exertion or at rest, orthopnea, rales, jugular venous pulse (JVP), peripheral edema, and the patient's assessment of dyspnea (Refer to [Section 16 Appendix 3](#)). These evaluations will be done at baseline, 6, 24 and 48 hours from start of study drug infusion, and then daily while hospitalized through Day 5, at Discharge, and Days 14 and 60. These evaluations should be done at approximately the same time of day, each day, in the same position, and hospital/clinic setting, preferably by the same assessor. To ensure consistency, if the same assessor cannot perform the daily assessments, the second assessor should evaluate the patient together with the first assessor at least once prior to performing the assessments independently.

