2.1.10.1 IV loop diuretic medications

IV loop diuretic medications include the following:

- Bumetanide

- Etacrynic acid/Ethacrynic acid
- Furosemide
- Torasemide/Torseamide

The number and percentage of subjects using IV loop diuretic medications will be summarized for each of the time periods: Hour 24/Day 1 to end of study, Hour 0/Day 1, 24 hours/Day 1, 48 hours/Day 2, Day 3, Day 4, Day 5, and Discharge. Each time point reflects medication use within the preceding 24 hours.

The average total daily dose for each medication will also be presented at reported time point. In addition, cumulative use reported at 48 Hours (24 hours/Day 1 and 48 hours/Day 2), and at Day 5 (from 24 hours/Day 1 to Day 5) in furosemide equivalent (mg) will be summarized. The calculation of furosemide equivalents (mg) for Bumetanide, Ethacrynic acid/Ethacrynic acid and Torsemide/Torseamide acid are actual dose (mg) multiplied by constant 40, 0.8, or 2, respectively. For subjects who die before Day 5, the minimum of 2 times of the last recorded dose and 160 mg will be assumed for every day from the date of death up to and including Day 5.

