2.2.1 Efficacy variables

The following table gives an overview of efficacy variables.

Table 2-5 Primary, secondary and exploratory variables

Variables	Analysis set	Analysis method
Primary efficacy variables		
1 Time to CV death through Day 180	FAS/PPS	log rank test and Kaplan-Meier estimates
2 Time to worsening heart failure (WHF) through Day 5 (considering death in the 5-day period as WHF event)	FAS/PPS	Gehan’s generalized Wilcoxon test
Secondary efficacy variables (if either primary variable is significant, follow sequential testing procedure)		
1 Time to all-cause death through Day 180	FAS/PPS	log rank test and Kaplan-Meier estimates (of note: will not be formally incorporated in a multiple testing procedure)
2 Length of total hospital stay (LOS) during the index AHF hospitalization	FAS/PPS	Wilcoxon rank-sum test
3 Time to first occurrence of the composite endpoint of CV death or rehospitalization due to heart failure (HF)/renal failure (RF) through Day 180	FAS/PPS	log rank test and Kaplan-Meier estimates
Other secondary efficacy endpoints (at $\alpha=0.05$, no multiplicity adjustment)		

Variables	Analysis set	Analysis method
1 Length of ICU and/or CCU stay for the index AHF hospitalization	FAS	Wilcoxon rank-sum test
2 Change from baseline in congestive signs and symptoms of HF through Day 5	FAS	Wilcoxon rank-sum test at each post-baseline visit
3 Change from baseline in selected biomarkers from baseline through Day 14 in a subset of randomized subjects	FAS	Repeated measurement model

Primary and key secondary endpoints are considered in sequential testing procedure and efficacy interim analysis

For the time to **confirmed** CV death during the follow-up period of 180 days, the confirmation of primary events is based on an adjudication process through an independent CEC (Clinical Endpoint Committee). The CEC will also adjudicate all recurrent events of the unplanned hospitalizations according to the protocol.

2.2.2 Definition of time to CV death through Day 180

Events that occur prior to or at the subject's final visit date will be part of the time-to-event analyses. Events that occurred more than 180 days will be considered as censored from the analyses. The CV death will be based on adjudicated results. If the adjudicated cause of death is unknown, it will be considered as a CV death.

The time-to-event for a given subject will be calculated as the difference between the subject's date of endpoint and the randomization date:

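### The day-level clock in SAP 2.2.7.2 lets a later WHF event or death overwrite a sign or symptom score recorded earlier the same day, and ties Hour 6 with Hour 24 responses

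*SAP*

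**What the plan says.** Protocol 6.4.4.1 fixes the assessment times: "These evaluations will be done at baseline, 6, 24 and 48 hours from start of study drug infusion", then daily while in hospital through Day 5. The column headings of Table 6-1 put both Hour 6 and Hour 24 in Day 1. SAP 2.1.10.1 uses the same convention ("24 hours/Day 1, 48 hours/Day 2").

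SAP 2.2.7.2 sets out two treatment comparisons for these scores.

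- **Responder analysis.** This is a Cox model with "response defined as ≥ 1 point improvement from baseline"; hazard ratios are "estimated using a Cox regression model stratified by region with treatment as a factor". On timing, "the nominal scheduled day will be used directly to determine the time to event with exact handling of ties". Patients without a response are censored at 6 days, withdrawal of consent or last contact, whichever is earliest.
- **By-visit analysis.** "Treatment groups will be compared with respect to change from baseline at each time point using Wilcoxon rank sum tests". Table 2-5 names this as the method for the endpoint: "Wilcoxon rank-sum test at each post-baseline visit".

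The same section assigns the worst score observed in any subject to patients who have WHF or die, "carried forward from the day of death or WHF regardless of whether their original data are missing", through Day 5. It does not limit this rule to one of the two analyses.

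**The concern.** Both rules use the day as their unit, although Day 1 holds two assessments and the order of assessments and events within a day can be known.

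The imputation rule is the more serious part. A score recorded before WHF is a valid observation of a patient who had not yet worsened. Replacing it moves information from a later event back to an earlier visit. The trial is designed to show that WHF differs between arms, so the replacement need not balance out. A WHF difference after Hour 6 could be read as a symptom difference at Hour 6.

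The timing rule matters less. If Hours 6 and 24 share one event time, the responder hazard ratio cannot show that relief came earlier within the first day. Exact handling of ties averages over the possible orderings and does not restore the one observed.

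What is at stake is the interpretation of a stated secondary objective, relief of congestion through Day 5.

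**Working it through.** The documents give no power or effect size for this endpoint, so there is no plan figure to reproduce.

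**1. Visit mapping.** Hours 6 and 24 map to Day 1. Hours 48, 72, 96 and 120 map to Days 2, 3, 4 and 5. Six assessments give five event times.

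**2. Imputation, by example.** A patient improves by one point at Hour 6 and has WHF at hour 20.

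- With nominal days, both fall in Day 1. The Hour 6 score becomes the worst score, the Hour 6 Wilcoxon test uses that value, and the patient is no longer a responder.
- With calendar days, the outcome depends on whether midnight falls between the two times. A score at any visit can then be overwritten by WHF later on the same date.
- By contrast, a patient who improves at Hour 24 and has WHF at hour 60 keeps the Hour 24 score and stays a responder. The plan thus respects the order of events across days but not within a day.

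**3. Exposure at Hour 6 (nominal-day reading).** Inputs are the placebo WHF rate of 12.2% and hazard ratios of 0.80 and 0.70 (SAP Table 2-10), and 6,800/2 = 3,400 per arm. The documents do not give the share of events between Hours 6 and 24. I assume an even spread over 120 hours, 18/120 = 15%, and ignore the gap of up to 4 hours between randomization and infusion.

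- Placebo: 0.122 × 0.15 × 3,400 = 62 patients.
- Hazard ratio 0.80: 1 − 0.878^0.80 = 9.9%; × 0.15 × 3,400 = 50.
- Hazard ratio 0.70: 1 − 0.878^0.70 = 8.7%; × 0.15 × 3,400 = 44.

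The difference is 12 to 18 patients, or 0.35 to 0.52 percentage points of each arm, all moved to the worst score. With a share of 5% the counts are 21 against 15 to 17; with 30% they are 124 against 89 to 101.

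**4. Power of the responder analysis.** Assumed placebo response hazards in the six intervals are 25/40/35/25/20/15%. The serelaxin hazard is 1 − (1 − h)^HR in the intervals where the effect applies. The test is an unstratified log-rank test without censoring, two-sided 0.05. With r the proportion still at risk in each arm, e the proportion responding in the serelaxin arm, and q the pooled hazard, Z = Σ n(e − r_s·q) / √[Σ n·r_p·r_s/(r_p + r_s)·q(1 − q)], and power ≈ Φ(Z − 1.96).

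| Effect | Hour-level | Day-level |
|---|---|---|
| HR 1.20, hours 0–6 only | 62% (Z 2.27) | 34% (Z 1.54) |
| HR 1.15, hours 0–6 only | 40% | 21% |
| HR 1.20, hours 6–24 only | 66% (Z 2.38) | 77% (Z 2.69) |
| HR 1.15, hours 6–24 only | 44% | 53% |
| HR 1.10, from Hour 6 onward | 71% | 80% |
| HR 1.08 throughout | 83% | 82% |
| 3–5 points more at Hour 6, equal by Hour 24 | 10–18% | 5% |

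A score test weighted for grouped times gives the same pattern: 59% against 39% for the first row and 73% against 84% for the third.

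I also varied the placebo response over 15–40% at Hour 6 and 50–70% at Hour 24, with 92% by Day 5. Under a constant hazard ratio of 1.05 to 1.10, the merged analysis keeps 93–99% of the information. The largest power difference is about 3 points (48.0% against 45.3%).

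**5. What the by-visit test still sees.** Take 25% against 29% responders at Hour 6 and a two-proportion test as a stand-in for the Wilcoxon test. Then Z = 0.04/√[(0.25 × 0.75 + 0.29 × 0.71)/3,400] = 3.72, and power is Φ(3.72 − 1.96) = 96%.

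**The case against.** A reader might infer that the plan discards the Hour 6 data. It does not. An Hour 6 response counts as a Day 1 event, and the Hour 6 scores are displayed and tested by visit. That test is the method named in Table 2-5, and step 5 shows it is strong where the day-level hazard ratio is weak.

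A reader might also infer that day-level timing always biases towards no difference, or that hour-level timing can only help. Step 4 contradicts both. When the effect falls only after Hour 6, the Hour 6 event time adds variance without signal, and the day-level test is stronger. When response is only brought forward within Day 1, the hour-level test remains weak.

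The tie is read from the visit labels. SAP 2.2.7.2 never says how an Hour 6 response is coded, and its use of day in the imputation rule may mean a nominal or a calendar day. The SAP's document history says the imputation was clarified to align with RELAX-AHF, and comparability is a fair aim. Counting WHF as a symptom failure is also a defensible choice.

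All this limits the timing point. It does not remove the imputation point. Either meaning of day allows an earlier score to be overwritten, and the rule has no exemption for the by-visit test, so that test cannot be offered as an untouched safeguard. Assigning the worst score after WHF does not require replacing scores measured before it.

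**Conclusion.** The point holds as two drafting defects in an other secondary endpoint tested at 0.05 without multiplicity adjustment. No confirmatory conclusion depends on it.

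The imputation defect is the stronger. As written, same-day scores that precede WHF or death are replaced, in both the by-visit tests and the responder analysis. If serelaxin reduces WHF, the replacement favours serelaxin at a visit before the events occurred; if it increases WHF, the reverse. Under an even spread of events this touches about 1.8% of placebo patients and 1.3–1.5% of serelaxin patients at Hour 6. That figure rests on the assumed timing of WHF.

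The timing defect is narrower: the responder hazard ratio cannot show earlier relief within Day 1. The case for correcting it is that the analysis should use the recorded order and that two programmers should derive the same event time. It is not that power always rises. All response rates behind the power figures are assumptions.

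**What to change.** Two changes to SAP 2.2.7.2.

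1. Apply worst-score imputation only to assessments after the date and time of WHF or death, and keep observed scores from before that time. SAP 2.2.3 already uses the WHF date and time for the primary endpoint. Compare date-time stamps rather than elapsed hours, because WHF is timed from randomization and the scores from the start of infusion. If an assessment time is missing, use its scheduled time.
2. Use the nominal scheduled hours (6, 24, 48, 72, 96, 120) as event times, and put censoring on the same scale. State that this is an exception to the general rule in SAP section 2 that time-to-event analyses use actual dates and times. If the Day 1 tie is intended, say so and refer to the by-visit test for Hour 6.

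The cost is SAP wording and a small derivation change before unblinding, with no new data. The second change may lose about 10 points of power if the effect begins only after Hour 6. The first departs from RELAX-AHF only if that study also overwrote same-day scores, which the documents do not say; a sensitivity analysis under the present rule would preserve comparability.
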